Historical Experience and Goals: Based on the historical experience in which the mean survival time was 8 months, under a Bayesian model we assume that the unadjusted mean survival time with TKI258 follows an uninformative inverse gamma with mean 8 and variance 1000, equivalently with scale parameter 2.064 and shape parameter 8.512, denoted mE ~ IG(2.064, 8.512). A mean survival time on average > 10 months would be considered promising evidence of anti-disease activity. Formally, assuming that the historical mean survival mH ~ IG(52, 400), TKI258 will be considered promising if, based on the data from the trial, Pr(mE > mH | data) > .95. The planned sample size is 40 patients, with an anticipated accrual rate of 3 patients per month. In addition, the relationships between several potential prognostic covariates and the above clinical outcomes will be explored, as described below.

Monitoring Rules: No early stopping rule in terms of the probability of PSA response will be employed because it is not known whether blocking the stromal-epithelial interactive pathway (SE-pathway) will be related to clinical benefit. Consequently, it may be the case that PSA does not drop but survival time is prolonged due to inhibition of disease progression by TKI258. Given the short survival time of these patients and anticipated accrual rate of 3 patients per month, it will not be feasible to implement an early stopping rule in terms of observed survival times. However, based on an historical rate of 20% grade 3 or 4 toxicity with standard therapies, it will be assumed that p = Prob(grade 3 or 4 with TKI258) follows a beta prior with parameters (.20, .80). Using the method of Thall and Suung (26), based on the observed toxicity data, accrual to the trial will be stopped early if Pr(p > .20 | data) > .95, with this rule applied after successive cohorts f size 5. This rule says to stop the trial if [# patients with a grade 3 or 4 toxicity]/[# patients evaluated] is greater than or equal to 3/5, 5/10, 7/15, 8/20, 9/25, 11/30, 12/35. The operating characteristics of this rule are summarized in the following table.

True Prob(toxicity)	Prob(Stop Early)	Achieved Sample Size
		$25^{\text{th}}, 50^{\text{th}}, 75^{\text{th}}$ percentiles

.10	.01	40 40 40
.20	.11	40 40 40
.30	.47	20 40 40
.40	.86	5 15 25

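### At 15 patients the toxicity formula stops accrual at 6/15, but the boundary list given as the same rule stops only at 7/15

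*Combined protocol and SAP*

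**What the plan says.** The monitoring rules appear in the synopsis and, in the same words, in Section 10.0. Both give the probability of grade 3 or 4 toxicity a beta prior with parameters .20 and .80. The comparison rate is a fixed .20, "based on an historical rate of 20% grade 3 or 4 toxicity with standard therapies". The criterion is that "accrual to the trial will be stopped early if Pr(p > .20 | data) > .95", "with this rule applied after successive cohorts f size 5" (that is, of size 5).

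The text then restates the criterion as counts. "This rule says to stop the trial if" the number with a grade 3 or 4 toxicity over the number evaluated "is greater than or equal to 3/5, 5/10, 7/15, 8/20, 9/25, 11/30, 12/35".

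Section 10.0 alone adds: "The operating characteristics of this rule are summarized in the following table". For true toxicity rates .10, .20, .30 and .40 the table prints early stopping probabilities of .01, .11, .47 and .86. The printed quartiles of sample size are 40/40/40, 40/40/40, 20/40/40 and 5/15/25. The maximum is 40 patients.

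**The concern.** The list is introduced as the formula in another form, so each fraction should be the smallest count at which the posterior probability exceeds .95. If one fraction is not, the plan contains two rules that differ at that look, with no statement of precedence.

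The plan expressly declines to stop early on PSA response or on survival, so toxicity is the only formal ground for stopping accrual early. Two people applying Section 10 correctly, one computing the posterior and one reading the list, would reach opposite accrual decisions at 6/15.

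**Working it through.** **Inputs, all from Section 10.0.** Prior Beta(.20, .80); fixed comparison rate .20; cut-off .95 with strict inequality; looks at n = 5, 10, ..., 35; maximum 40.

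**Formula.** After x toxicities in n patients the posterior is Beta(.20 + x, .80 + n − x). The boundary is the smallest x with Pr(p > .20) > .95.

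| n | Listed x | Pr at listed x | Pr at one fewer | Boundary from formula |
|---|---|---|---|---|
| 5 | 3 | .9602 | .7965 | 3 |
| 10 | 5 | .9757 | .9044 | 5 |
| 15 | 7 | .9862 | **.9513** | **6** |
| 20 | 8 | .9742 | .9279 | 8 |
| 25 | 9 | .9612 | .9068 | 9 |
| 30 | 11 | .9788 | .9481 | 11 |
| 35 | 12 | .9710 | .9355 | 12 |

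Six boundaries reproduce, which indicates that the prior and criterion are being read as meant. At n = 15 the posterior after six toxicities is Beta(6.2, 9.8), with Pr(p > .20) = .9513. After five it is .8628. The formula's boundary is therefore 6/15.

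**What would give the printed list.** With the stated prior, 6/15 must not stop, so the cut-off must be at least .95126. 3/5 must stop, so the cut-off must be below .96021. Any cut-off from .9513 to just under .9602 gives all seven printed fractions. So does rounding the posterior to two decimals before comparing it with .95. So does replacing the fixed .20 by a beta-distributed historical rate such as Beta(40, 160), although Beta(20, 80) and Beta(2000, 8000) do not. The plan states none of these.

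**Operating characteristics.** These are exact: binomial convolution over cohorts of 5, maximum 40.

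| True rate | Printed stop prob. | List (7/15) | Formula (6/15) | Printed quartiles | List quartiles | Formula quartiles |
|---|---|---|---|---|---|---|
| .10 | .01 | .010 | .011 | 40/40/40 | 40/40/40 | 40/40/40 |
| .20 | .11 | .117 | .131 | 40/40/40 | 40/40/40 | 40/40/40 |
| .30 | .47 | .488 | .509 | 20/40/40 | 15/40/40 | 15/35/40 |
| .40 | .86 | .865 | .873 | 5/15/25 | 5/15/25 | 5/15/25 |

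The list matches 11 of the 12 printed quartiles and the formula 10. The list's one miss is the 25th percentile at .30. Its stopping probability by n = 15 is .1631 + .0618 + .0322 = .257, which puts that percentile at 15. Under the formula the corresponding sum is .1631 + .0618 + .1171 = .342.

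**Consequences of the difference.**

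| True rate | Mean sample size, list / formula | Chance of exactly 6/15, no earlier stop | From 6/15, list stops later | From 6/15, mean further patients under list |
|---|---|---|---|---|
| .20 | 36.8 / 36.4 | 2.5% | 43% | 17.6 |
| .30 | 28.4 / 27.4 | 8.5% | 76% | 12.0 |
| .40 | 17.9 / 16.9 | 11.9% | 94% | 8.2 |

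The last column counts enrolment to 40 when the list never stops. As a check at .30, the two rules differ only on paths through 6/15 that the list never stops later: .0849 × (1 − .7569) = .0206 = .5088 − .4882.

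**The case against.** The best reply is that the list is the working rule. It is an explicit count rule, printed identically in two places, and staff would meet a conflict only by recomputing the posterior. The excess over .95 is .0013, which disappears if the posterior is rounded to the two decimals of the cut-off.

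The table also follows the list. Every stopping probability is within 2 points of the list's exact value, and the printed median of 40 at .30 agrees with the list and not with the formula's 35. The 25th percentile of 20 at .30 is a near miss for the list (.257 against .25) and a clear miss for the formula (.342). Simulation error could explain the residual gaps, though the plan does not say how the table was obtained. If it came from 1,000 runs (an assumption), the standard error at .30 is √(.488 × .512 / 1,000) = .016, and .47 lies about 1.1 standard errors from .488. With 10,000 runs the standard error is .005 and the gap is about 3.6, which chance would not readily explain.

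Most of this stands. The table was probably computed from 7/15, and the practical effect is small. But a table computed from the list does not show that the list was what the designers intended, since a mistaken entry would have been carried into it. If the list was intended, the formula as written is wrong for it. The criterion is a strict inequality, and no rounding convention or order of precedence is given.

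**Conclusion.** The concern holds. As written, the formula and the list disagree at one look of seven: at 6/15 the formula stops accrual and the list does not. This rests only on the stated prior, the fixed .20 and the strict .95 cut-off.

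Taking the formula in place of the list raises the overall stopping probability by 1.4, 2.1 and 0.8 percentage points at true rates .20, .30 and .40, and lowers mean sample size by 0.4 to 1.0 patients. The conflict arises on a path with probability 2.5% to 11.9% over that range. It should be corrected because it leaves a decision open in the only formal early stopping rule, not because it changes the design's performance much. The documents do not show which version was intended, although the table leans towards the list.

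**What to change.** Reconcile the formula and list in the synopsis and Section 10.0, and the table in Section 10.0, and say which form governs. There are two ways, and the choice is the sponsor's.

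- **(a) Keep the formula.** Change 7/15 to 6/15. Restate the stopping probabilities as .01, .13, .51 and .87, with quartiles 15/35/40 at .30. The cost is one fraction and a few table entries. False stopping at a true rate of .20 rises from 11.7% to 13.1%.
- **(b) Keep the list.** State the definition that yields 7/15: a cut-off from .9513 to just under .9602 with the present prior, a rounding convention, or an explicit prior or historical-rate distribution. The exact table is then .01, .12, .49 and .87, with a 25th percentile of 15 at .30. If the printed entries came from simulation and are kept, say so and give the number of runs. The cost is one line of definition and, if restated, a few table entries. The listed rule's actual operating characteristics do not change.

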7.1 Screening Period (Days –30 to Day 1)

The following activities/procedures will be conducted during the screening period which may occur within 30 days prior to registration the following baseline evaluations shall be performed:

- Complete medical history must be available in the patient's medical record
- Chest X-ray
- CT or MRI scans of the pelvis and abdomen.
- Bone Scan
- Baseline (pre-treatment) bone marrow biopsy and aspiration within 30 days prior to registration. The specimens will be evaluated by pathology. A portion of bone marrow will be banked for bone marker testing. Patients who have undergone a bone marrow aspirate and biopsy outside the context of this clinical trial are eligible for the trial and may elect not to repeat these baseline studies if the samples were collected within 12 weeks prior to initiation of TKI258 therapy. If a portion of the tissue collected from a previous bone marrow aspirate and biopsy was banked for future use under Lab02-152, Lab03-0320, or another GU clinical trial, the tissue will be requested for this timepoint.
- Electrocardiogram (ECG)
- Echocardiogram or MUGA scan
- 7.2 Screening Period (Days –14 to Day 1)

The following activities/procedures will be conducted during the screening period which may occur within 14 days prior to registration the following baseline evaluations shall be performed:

- Interim medical history including demographics
- Oncology history
- Physical examination
- Vital signs including blood pressure, heart rate, respiratory rate, oral body temperature, weight and height.
- List of concurrent medications and baseline adverse events
- Assessment of ECOG Performance Status
- Laboratory testing:
 - CBC with differential/platelets
 - Serum chemistry must include: BUN, creatinine, total bilirubin, albumin, SGOT [AST], SGPT [ALT], GGT, LDH, amylase, lipase, alkaline phosphatase, fasting glucose, calcium, sodium, magnesium, phosphorus, and potassium
 - PSA assessment.
 - Serum testosterone and DHT levels.
 - Bone Specific Alkaline Phosphatase
 - Blood for Biomarker Studies
 - N-telopeptides in urine

Correlative Studies: Assessment of serum and bone marrow aspirate androgen levels, plus additional serum/plasma banking.

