Data Analysis. If the data on the 40 patients yield a sample mean of 10 months (the targeted 25% improvement) based on total follow-up time 400 months (all 40 deaths observed) then the posterior of m would be IG(42.064, 408.512), which has mean 9.95 months and posterior 95% credible interval 7.33 - 13.4 months. Similarly, if 35 deaths are observed with 5 death times administratively censored and total follow-up 460 months at the final analysis then the posterior of m would be IG(37.064, 468.512),), which has mean 13 months and posterior 95% credible interval 9.39 - 17.95 months. Unadjusted survival time will be estimated using the method of Kaplan and Meier (27). The effects of the following four potential prognostic covariates on Prob(PSA response) will be estimated using logistic regression (28), and on survival time will be estimated using the Cox model or, if the proportional hazards assumption is not satisfied, using an appropriate time-to-event regression model chosen based on preliminary goodness-of-fit analyses of the data (29). Each of the following covariates is a binary indicator.

- 1. Inhibition of FGF signaling by bone marrow biopsy at 4 weeks.
- 2. Modulation of the bone markers (a) urinary NTX and (b) bone specific alkaline phosphatase
- 3. Baseline signature of FGF signaling in temrs of FGF R-1, FGF R-3 and FGF 9.

Time of disease progression if defined by PSA alone is defined as follows: Three consecutive PSA elevations above nadir or baseline are required. Each increment in PSA should be a minimum of 1 ng/ml and at least 2 weeks apart or will not count. The time of PSA progression will be taken as the time of the first of these PSA elevations that represents an increment by at least 25% above the nadir or baseline. Given that increments in PSA do not always represent treatment failure, particularly when novel agents with uncertain effects on PSA levels are being evaluated, clinical and radiological correlation is recommended at the discretion of the treating physician. In patients with PSA progression alone without clinical or radiological evidence of disease progression, continued therapy on study is at the discretion of the treating physician in consultation with the principal investigator.

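### The marker models for PSA response and survival include no baseline clinical factor, so a marker that only tracks disease burden can appear linked to outcome; adding one or two collected factors would reduce this, but not remove it

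*Combined protocol and SAP*

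**What the plan says.** Section 10.0 (Data Analysis) sets out the marker models: "The effects of the following four potential prognostic covariates on Prob(PSA response) will be estimated using logistic regression (28), and on survival time" by the Cox model or another time-to-event regression. Section 10.0 and the Synopsis (Statistical Methods) give the same list of covariates for both models. Section 10.0 adds that "Each of the following covariates is a binary indicator". The list is:

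- "Inhibition of FGF signaling by bone marrow biopsy at 4 weeks";
- "Modulation of the bone markers (a) urinary NTX and (b) bone specific alkaline phosphatase", which counts as two;
- "Baseline signature of FGF signaling in temrs of FGF R-1, FGF R-3 and FGF 9".

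No section adds a clinical covariate, the starting level of urinary NTX or bone alkaline phosphatase, or an adjusted or sensitivity model. The text does not say whether the four markers enter one joint model or separate models.

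The candidates for adjustment are collected. Section 7.2 lists "Assessment of ECOG Performance Status", a blood count, serum chemistry with LDH and albumin, PSA, "Bone Specific Alkaline Phosphatase", urinary N-telopeptides and oncology history. Section 6.2 records previous treatments.

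The status of the analysis is exploratory: "the relationships between several potential prognostic covariates and the above clinical outcomes will be explored, as described below". Section 2.0 nevertheless makes the correlation of PSA modulation with bone-marker change a primary objective, and the predictive value of the FGF markers a secondary one.

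**The concern.** Baseline risk can vary widely here. Section 4.1 admits ECOG up to 2 and hemoglobin from 8.0 g/dL, and Section 4.2 admits prior chemotherapy after a four-week washout. All patients have skeletal metastases, and NTX and bone alkaline phosphatase are bone-turnover markers, so extent of bone disease is the obvious rival explanation for any association with outcome. With one arm, no control group can separate a drug-related marker effect from background prognosis. Baseline adjustment is the main safeguard available, and the plan names none.

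At stake is which markers are carried forward as informative about TKI258. The formal survival criterion does not use these models and is unaffected.

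**Working it through.** **1. The plan's own figures.** Nothing is stated for alpha, power or effect size in the marker models. The nearest figures are the two survival posteriors in Section 10.0, which fix the number of deaths. The update adds deaths to the first parameter and months of follow-up to the second; the mean is b/(a-1).

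- 40 deaths, 400 months: (2.064+40, 8.512+400) = (42.064, 408.512). Mean 408.512/41.064 = 9.95; 95% interval 7.33 to 13.47 (the plan prints 13.4).
- 35 deaths, 460 months: (37.064, 468.512). Mean 468.512/36.064 = 12.99; interval 9.39 to 17.95.

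Both reproduce, so 35 to 40 deaths is the working range.

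**2. Event budget.** Four terms use 40/4 = 10 or 35/4 = 8.75 deaths per term. Section 10.0 expects about 60% positive biopsies: 0.60 × 40 = 24 patients. At the same death fractions that is 21 to 24 deaths, or 5.3 to 6 per term with four terms. If PSA response is 20-40% (assumed), there are 8 to 16 responders, or 2 to 4 per term.

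**3. Expected size of the spurious effect.** Assumptions: a 50/50 marker with no effect of its own, correlation r between its underlying score and a standardised burden score, and hazard ratio h per SD of burden. The mean burden difference between marker groups is 2r√(2/π) = 1.596r. The approximate spurious log hazard ratio is 1.596r × ln h:

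- r=0.3, h=1.5: 0.479 × 0.405 = 0.194, HR 1.21
- r=0.5, h=1.5: 0.798 × 0.405 = 0.324, HR 1.38
- r=0.3, h=2.0: 0.479 × 0.693 = 0.332, HR 1.39
- r=0.5, h=2.0: 0.798 × 0.693 = 0.553, HR 1.74

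This slightly overstates what a Cox model returns, because burden left out of the model pulls the estimate toward 1.

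**4. Simulation, Cox.** Exponential survival with mean 8 months at average burden, two-sided 5% Wald test, 2,000 trials per cell. There were 40 patients with 12.5% censored (35 deaths):

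| r | h | Unadjusted: p<0.05 | Unadjusted: median HR | Adjusted for true burden: p<0.05 | Adjusted: median HR |
|---|---|---|---|---|---|
| 0.3 | 1.5 | 7.4% | 1.21 | 6.3% | 1.00 |
| 0.5 | 1.5 | 12.4% | 1.35 | 5.6% | 1.00 |
| 0.3 | 2.0 | 13.0% | 1.32 | 5.9% | 1.00 |
| 0.5 | 2.0 | 26.0% | 1.56 | 5.2% | 0.99 |

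With all 40 deaths observed, repeated runs put the unadjusted rate at about 9-28% over the same cells. At r=0 the rate is 5-6%, so the excess comes from the correlation.

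**5. Realistic adjustment.** ECOG and LDH are imperfect stand-ins for burden. With two proxies, each correlated 0.6 with burden (assumed), and 40 patients, the rate falls from 10-28% to 8-13%, and the spurious HR from 1.18-1.58 to 1.08-1.32. With 24 patients the rate is 7-19% unadjusted and 7-11% adjusted. One proxy, 40 patients: 27% to 16% (HR 1.57 to 1.40) in the strong cell; 8% unchanged (HR 1.21 to 1.14) in the weak cell.

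**6. Too many terms.** In the weak cell, one proxy plus three uninformative terms raises the rate from 8% to 11% with 40 patients, and from 7-8% to 12% with 24.

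**7. Logistic model.** Assumptions: odds ratio 0.5 per SD of burden, response 20% or 40%, r=0.5 to 0.7. The unadjusted rate is 7-19% with 40 patients and 2-11% with 24. Adjusted for true burden it is 3-4% and 1-3%.

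**8. Starting value of a change marker.** Under pure measurement error, an unadjusted change marker showed no bias (HR 1.02, 5.5% significant). Adding its own baseline created bias (HR 0.73, 15%). Where high values truly regress, the same adjustment helped.

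**The case against.** The strongest reply is that this is declared exploration. No decision, alpha or claim of independent effect rests on these models, and univariable screening is legitimate with 40 patients. A marker that tracks burden is also truly prognostic in the unadjusted sense. This stands as far as it goes: what cannot be claimed from the planned models is independent prognostic value or a drug-mechanism effect. It does not remove the point, because Section 2.0 makes the predictive value of the FGF markers an objective.

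A second reply is that adjustment promises more than it delivers. That also stands. A return to about 5% and a hazard ratio of 1.0 requires a burden score measured without error; realistic proxies do less, and extra terms can do harm.

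Three stronger readings are tempting, and the documents do not support them:

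- **The models contain no baseline marker at all.** A baseline FGF signature is one of the four covariates. What is missing is any clinical factor and the starting NTX and bone alkaline phosphatase levels.
- **A burden marker will come out as prognostic.** Across the 40-death range such a marker is non-significant in about 72-91% of trials (100 minus 28, 100 minus 9).
- **Regression to the mean obliges adjustment of each change marker for its own baseline.** Step 8 shows that this can create bias as well as remove it, and the documents do not say which situation applies.

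**Conclusion.** The point holds in a limited form. Both marker models omit every baseline clinical factor although suitable ones are collected, and in this single-arm, mixed-risk population that lets a proxy for burden appear linked to outcome. For survival with 40 deaths, the false-positive rate is about 9-28% against a nominal 5%. Two imperfect proxies bring it to about 8-13% and leave part of the spurious hazard ratio. With 24 patients the gain is smaller. For PSA response the inflation is smaller and was examined only at correlations of 0.5 to 0.7.

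All correlations, burden effects, proxy strengths, the 50/50 split and PSA response rates are assumptions. The direction of the result follows from the design; its size depends on those inputs.

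**What to change.** Add to Section 10.0 and the Synopsis:

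- Fit each marker separately. Beside the unadjusted Cox estimate, report one adjusted for one or two prespecified baseline factors, for example ECOG and LDH.
- Use one baseline factor only in the logistic model, and in any analysis limited to the roughly 60% of patients with positive biopsies.
- Describe unadjusted associations as not independent of disease burden.
- Show models that add baseline NTX or bone alkaline phosphatase to the matching change marker as sensitivity analyses only.

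The timing of the on-treatment biopsy must also be reconciled before the FGF-inhibition covariate is defined: Section 10.0 gives 4 weeks, the Synopsis 8 weeks, and Section 7.4.5 between 7 and 10 weeks.

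The cost is SAP wording, with no new samples, visits or patients. The downside is slightly wider intervals, and residual confounding that should be acknowledged in the report.

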TKI258 500mg PO daily for 5 days, followed by a 2 day rest period. Each cycle is 28 days.

Duration of Treatment:

Patients will continue to receive TKI 258 until progression, unacceptable toxicity or withdrawal of consent

Statistical Methods:

This is a phase IIA activity trial of TKI 258 for treatment of castrate resistant prostate cancer with skeletal metastases. The two primary outcomes are survival time and early response as characterized by a drop in PSA as defined by Prostate Cancer Working Group 2 criteria. Based on a historical mean survival of time 8 months, a mean survival time on average > 10 months with TKI258 would be considered promising evidence of anti-disease activity. The planned sample size is 40 patients, with an anticipated accrual rate of 3

patients per month. Based on historical experience using carefully selected candidates with evidence for iliac involvement on bone scan, we anticipate that ~60% of patients will have positive biopsies. No early stopping rule in terms of the probability of PSA response will be employed because blocking the stromal-epithelial interactive pathway (SE-pathway) may produce clinical benefit independent of PSA modulation. Consequently, it may be the case that TKI258 does not cause significant reductions in PSA, but survival time is prolonged due to inhibition of disease progression. Given the short survival time of these patients and anticipated accrual rate of 3 patients per month, it also will not be feasible to implement an early stopping rule in terms of observed survival times. Based on an historical rate of 20% grade 3 or 4 toxicity with standard therapies the method of Thall and Sung (1998) will be used to monitor toxicity.

Unadjusted survival time will be estimated using the method of Kaplan and Meier (1958) and the effects of the following four potential prognostic covariates Inhibition of FGF signaling by bone marrow biopsy at 8 weeks, modulation of the bone markers (a) urinary NTX and (b) bone specific alkaline phosphatase, and baseline signature of FGF signaling in terms of FGF R-1, FGF R-3 and FGF 9 on Prob(PSA response) will be estimated using logistic regression, and on survival time will be estimated using the Cox model or an appropriate time-to-event regression model.

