2.0 STUDY OBJECTIVES

2.1 Primary Objective

The primary objective of this study is:

- To estimate overall survival and early response as characterized by a drop in PSA
- To identify the PSA modulation in 40 selected patients with advanced prostate cancer, and to correlate PSA Modulation with changes in bone remodeling markers.

Secondary Objectives

The secondary objectives of this study are:

- To estimate the objective tumor response rate for subjects with measurable disease at baseline.
- To explore the potential association between serum PSA and bone turnover markers with bone marrow FGF R 1 and FGF9 while on TKI 258
- To explore the predictive values of baseline FGF R 1, FGF9, and FGF signaling in serum and those in the bone marrow before and during treatment with TKI258
- To identify candidate mRNA gene expression changes in bone marrow biopsy aspirate following treatment with TKI258
- To collect and archive bone marrow biopsies and aspirates, serum and plasma in study patients for later hypothesis generating associations
- To explore FGF R expression following eight weeks of TKI 258.

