10.0 PLANNED STATISTICAL METHODS

This is a phase IIA activity trial of TKI258 for treatment of castrate resistant prostate cancer with skeletal metastases. The two primary outcomes are survival time and early response as characterized by a drop in PSA as defined by working group criteria. Based on historical mean survival time 8 months, a mean survival time on average > 10 months with TKI258 would be considered promising evidence of anti-disease activity. The planned sample size is 40 patients, with an anticipated accrual rate of 3 patients per month. Based on historical experience using carefully selected candidates with evidence for iliac involvement on bone scan, we anticipate that ~60% of patients will have positive biopsies. No early stopping rule in terms of the probability of PSA response will be employed because it is not known whether blocking the stromal-epithelial interactive pathway (SE-pathway) will be related to clinical benefit. Consequently, it may be the case that PSA does not drop but survival time is prolonged due to inhibition of disease progression by TKI258. Given the short survival time of these patients and anticipated accrual rate of 3 patients per month, it also will not be

feasible to implement an early stopping rule in terms of observed survival times. Based on an historical rate of 20% grade 3 or 4 toxicity with standard therapies the method of Thall and Sung (1998) will be used to monitor toxicity. Unadjusted survival time will be estimated using the method of Kaplan and Meier (1958) and the effects of the following four potential prognostic covariates: Inhibition of FGF signaling by bone marrow biopsy at 4 weeks, modulation of the bone markers (a) urinary NTX and (b) bone specific alkaline phosphatase, and baseline signature of FGF signaling in terms of FGF R-1, FGF R-3 and FGF 9 on Prob(PSA response) will be estimated using logistic regression, and on survival time will be estimated using the Cox model or an appropriate time-to-event regression model.

Preliminaries: This is a phase IIA activity trial of TKI258 for treatment of castrate resistant prostate cancer with skeletal metastases. The two primary outcomes are survival time and early response as characterized by a drop in PSA as defined by working group criteria (25).

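### The primary objective relating PSA modulation to bone-marker change is analysed only as yes/no PSA response against yes/no markers, which discards much of the information and may fail if responders are few

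*Combined protocol and SAP*

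**What the plan says.** The Synopsis and Section 2.1 list two primary objectives. The first is to estimate survival and early PSA response. The second, a separate bullet, is to identify PSA modulation in 40 patients and "to correlate PSA Modulation with changes in bone remodeling markers".

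Section 10, Data Analysis, gives one analysis that relates PSA to the markers: "The effects of the following four potential prognostic covariates on Prob(PSA response) will be estimated using logistic regression". Two of the four covariates are the bone markers: "Modulation of the bone markers (a) urinary NTX and (b) bone specific alkaline phosphatase". On coding it says "Each of the following covariates is a binary indicator"; no cut-point is given. The Synopsis defines the PSA outcome as "early response as characterized by a drop in PSA as defined by Prostate Cancer Working Group 2 criteria". The same covariates also enter a Cox model, but for survival. The PSA-progression definition that closes Section 10 is not tied to any marker analysis.

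In explaining why there is no PSA stopping rule, the Synopsis says "it may be the case that TKI258 does not cause significant reductions in PSA", and Section 10 says "it may be the case that PSA does not drop but survival time is prolonged". On size: "The planned sample size is 40 patients". No PSA response rate is assumed anywhere for TKI258.

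Under Section 7.4, PSA is measured at Cycle 1 Day 1 and every 4 weeks. Urinary NTX and bone alkaline phosphatase are measured at Day 1, week 4, week 8 and every 8 weeks after that.

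**The concern.** The objective speaks of correlating a PSA quantity with marker changes. The analysis reduces both sides to yes/no. A patient whose PSA falls modestly, or rises more slowly, counts the same as one whose PSA climbs steeply. If PSA response is uncommon, which the plan accepts as possible, a logistic regression on 40 patients has little or nothing to work with, and no fallback is named. A primary objective could then go largely unanswered although serial PSA and marker values are in the database. A method chosen only after the sparse responses had been seen would be open to the charge of being post hoc.

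**Working it through.** **The plan's own precision figure.** The only precision shown for N = 40 concerns survival. Adding 40 deaths and 400 months to the prior gives IG(2.064 + 40, 8.512 + 400) = IG(42.064, 408.512). Its mean is 408.512 / 41.064 = 9.95 months, with a 95% interval of 7.33 to 13.47; the plan prints 9.95 and 7.33 to 13.4. It reproduces, but says nothing about PSA. No rate, power or precision is stated for PSA response or for its relation to the markers.

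**Inputs.** From the documents: N = 40, binary response, binary markers, mean survival 8 months. Assumed, because the documents give nothing: PSA response rate p of 5% to 45%; true correlation 0.5 between the two changes (bivariate normal); two-sided 5% level; markers split at the median, 20/20. The 45% end reflects the only human PSA response rate in the documents, 40 to 50% with docetaxel (Section 1.2), which is a different drug.

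**Step 1: information kept when PSA change is dichotomised.** Relative efficiency = φ(z)² / [p(1 − p)], where z cuts off the upper fraction p. For p = 0.10: z = 1.282, φ = 0.1755, so 0.0308 / 0.09 = 0.34.

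**Step 2: number of responders.** Binomial with n = 40.

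**Step 3: no finite odds ratio, with no true association.** One marker with 50% prevalence gives none when a cell of the 2×2 table is empty. For all four covariates in one model, separation was checked in 1,500 simulated trials per rate.

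| Response rate | Expected responders | Information kept | P(at most 4 responders) | No finite estimate, one marker | No finite estimate, four covariates together |
|---|---|---|---|---|---|
| 5% | 2 | 22% | 95% | 60% | 82% |
| 10% | 4 | 34% | 63% | 24% | 48% |
| 20% | 8 | 49% | 8% | 3% | 10% |
| 30% | 12 | 58% | 0.3% | 0.3% | 1% |
| 45% | 18 | 63% | about 0 | <0.1% | <0.1% |

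**Step 4: why 4 responders matters.** With a 20/20 marker split and all responders on one side, the two-sided Fisher p-value is 2·C(20,4)/C(40,4) = 2 × 4,845 / 91,390 = 0.106 for 4 responders, and 2·C(20,5)/C(40,5) = 2 × 15,504 / 658,008 = 0.047 for 5. With 4 or fewer, no pattern reaches 5%.

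**Step 5: power at correlation 0.5, n = 40.**
- Both changes continuous: atanh(0.5) × √37 = 0.549 × 6.083 = 3.34; Φ(3.34 − 1.96) = 0.92. This is for the ordinary correlation; a rank correlation would be slightly lower.
- PSA continuous, marker median-split: 0.75 (simulation).
- PSA binary, marker continuous: 0.29, 0.44, 0.61 and 0.70 at rates of 5%, 10%, 20% and 30%.
- Both binary, the plan's coding: about 0.07, 0.25, 0.42 and 0.52 at 5%, 10%, 20% and 30% with the usual approximate test. With Fisher's exact test: 0.02, 0.14 and 0.32 at 5%, 10% and 20%, and 0.43 at 45%.

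**Step 6: patients available at week 8.** Assuming exponential survival, which the inverse-gamma updating of deaths and follow-up time implies, with mean 8 months: 56 days = 1.84 months, exp(−1.84/8) = 0.79, and 40 × 0.79 ≈ 32 alive. Continuous power is then about 0.85. Other withdrawals would reduce it further. The binary analysis also needs an on-treatment marker value, so it does not escape this loss.

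**The case against.** Several points against the concern carry weight.

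- **The plan does not predict a low response rate.** A reader might infer from the stopping-rule rationale that few responders are expected. The Synopsis and Section 10 only say that PSA may not drop, and give no rate. This stands.
- **PSA modulation is never defined as a graded quantity.** The Synopsis uses response and modulation almost interchangeably in one sentence, and Section 10 treats bone-marker modulation as yes/no. On that reading the logistic regression does address the objective, so it would be wrong to say the objective has no analysis. The separate objective bullets, and the words about correlating with changes, still favour a graded reading. The matter is one of a weak method and an undefined term.
- **At the docetaxel rates the model can be fitted.** This stands: at 45% a finite fit is almost certain. About 37% of the information is still lost on the PSA side.
- **A single four-covariate model is an inference.** Section 10 does not say that the covariates enter together. The one-marker column above does not depend on it.
- **The 0.92 owes part of its size to continuous markers.** With the plan's binary markers, continuous PSA gives 0.75. The gain from 0.75 to 0.92 comes from changing the marker coding as well.
- **The covariate work is described as exploratory.** True of Section 10, but the Synopsis and Section 2.1 place this correlation among the primary objectives.

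**Conclusion.** The concern holds in a limited form. The analysis that serves this primary objective dichotomises both sides. On the PSA side alone it keeps roughly a fifth to two thirds of the information over response rates of 5% to 45%. At about 10% or lower it may have no finite estimate or no route to significance; from 20% upward it can usually be fitted but is imprecise. Under a correlation of 0.5 and n = 40, power is about 0.92 with both changes continuous, against 0.07 to 0.52 with the plan's coding at rates of 5% to 30%. With about 32 patients at week 8 the continuous figure is about 0.85.

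A reader might go further and call the objective unanswerable. The documents do not support that: it follows only if the response rate is very low, and they give no rate. The response rates, the correlation, the 5% level, the median split and exponential survival are all assumptions. The ordering of the methods at the rates examined does not depend on the exact values; the sizes do.

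**What to change.** In Section 10, Data Analysis:

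1. State what PSA modulation means for the second primary objective.
2. Add, as the analysis of that objective, a rank correlation with a confidence interval between log(PSA / baseline PSA) and the continuous change in urinary NTX, and likewise for bone alkaline phosphatase, at the same visit. Use week 8, with week 4 for patients who have no week 8 value. Report how many patients contribute, and from which visit.
3. Keep the PSA response proportion as the estimate of early response.
4. Keep the planned logistic regression, and name an exact or penalised fit for use if responders are few.

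The cost is SAP wording and one extra analysis of data already scheduled under Section 7.4; no new visit, sample or patient is needed. The limitation is that the result describes only patients with an on-treatment value, so early deaths and withdrawals are left out and should be counted beside it. The wording should be settled before PSA and marker data are examined together.
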